## 8.6 STABLE DISEASE

---

To satisfy criteria for SD, the following criteria must be met:

- No evidence of new disease
- There is neither sufficient evidence of tumor shrinkage to qualify for PR nor sufficient evidence of tumor growth to qualify for definitive PD

## 8.7 DEFINITIVE DISEASE PROGRESSION

---

The occurrence of any of the following events indicates definitive PD:

- Evidence of any new disease:
  - A new node that measures >1.5 cm in the LD and >1.0 cm in the LPD
  - New or recurrent splenomegaly, with a minimum LVD of 14 cm
  - New or recurrent hepatomegaly, with a minimum LVD of 20 cm
  - Unequivocal reappearance of an extra-nodal lesion that had resolved
  - A new unequivocal extra-nodal lesion of any size
  - \*New non-target disease (e.g., effusions, ascites, or other organ abnormalities related to CLL).

\*Isolated new effusions, ascites, or other organ abnormalities are not sufficient evidence alone of PD unless histologically confirmed. Thus, a declaration of PD should not be made if this is the only manifestation of apparently new disease.

- Evidence of worsening of target lesions, spleen or liver, or non-target disease:
  - Increase from the nadir by  $\geq 50\%$  from the nadir in the SPD of target lesions
  - Increase from the nadir by  $\geq 50\%$  in the LD of an individual node or extra-nodal mass that now has an LD of >1.5 cm and an LPD of > 1.0 cm
  - Splenic progression, defined as an increase in splenic enlargement by  $\geq 50\%$  from nadir (with a minimum 2 cm increase and a minimum LVD of 14 cm)
  - Hepatic progression, defined as an increase in hepatic enlargement by  $\geq 50\%$  from nadir (with a minimum 2 cm increase and minimum LVD of 20 cm)
  - Unequivocal increase in the size of non-target disease (e.g., effusions, ascites, or other organ abnormalities related to CLL)
  - Transformation to a more aggressive histology (e.g., Richter's syndrome) as established by biopsy (with the date of the biopsy being considered the date of CLL progression if the subject has no earlier objective documentation of CLL progression).
- Decrease in platelet count or hemoglobin that is attributable to CLL, is not attributable to an autoimmune phenomenon, and is confirmed by bone marrow biopsy showing an infiltrate of clonal CLL cells
  - The current platelet count is  $< 100 \times 10^9/L$  and there has been a decrease by  $> 50\%$  from the highest on-study platelet count
  - The current hemoglobin is  $< 110 \text{ g/L}$  (11.0 g/dL) and there has been a decrease by  $> 20 \text{ g/L}$  (2 g/dL) from the highest on-study hemoglobin

Worsening of disease during temporary interruption of study treatment (e.g., for intercurrent illness) is not necessarily indicative of resistance to study treatment. In these instances, CT/MRI or other relevant evaluations should be considered in order to document whether definitive disease progression has occurred. If subsequent evaluations suggest that the subject has experienced persistent definitive CLL progression, then the date of progression should be the timepoint at which progression was first objectively documented.

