#### 8.2.1 TARGET LESIONS

---

At baseline, up to 6 lymph nodes should be selected as target lesions that will be used to quantitate the status of the disease during study treatment. Ideally, the target lesions should be located in disparate regions of the body. Only peripheral nodes need be selected as target lesions. However, it

is optimal if mediastinal and retroperitoneal areas of disease are assessed whenever these sites are involved.

Target lesions will be measured and recorded at baseline and as per the study assessment schedule. The cross-sectional dimensions (the largest cross-sectional diameter, i.e., the LD × LPD) will be recorded (in cm) for each target lesion. The product of the perpendicular diameters (PPD) (in cm^2) for each target lesion and the sum of the products (SPD) (in cm^2) for all target lesions will be calculated and recorded. The baseline SPD will be used as references by which objective tumor response will be characterized during treatment. The nadir LD of individual lesions and the nadir SPD will be used as references by which CLL progression will be characterized. All LD and LPD diameters will be reported in centimeters and all PPDs and SPDs will be reported in centimeters squared.

A nodal mass may be selected as a nodal target lesion if it is both abnormal and measurable at baseline. A lymph node lesion is considered abnormal if it has a single diameter that is > 1.5 cm and is considered measurable if it has 2 perpendicular diameters that can be accurately measured in cross section with the LD being ≥ 1.0 cm and the LPD also being ≥ 1.0 cm.

A new node that measures >1.5 cm in the LD and >1.0 cm in the LPD will be considered progressive disease.

In cases in which a large lymph node mass has split into multiple components, all subcomponents regardless of size will be used in calculating the SPD. Progression of the lesion will be based on the SPD of sub-components. Lesion sub-components will have the true PPDs calculated. Similarly, lesion sub-components that are visible but neither abnormal nor measurable will have the default PPD of 1.0 cm^2 (1.0 cm × 1.0 cm) used in calculating the SPD.

If lesions merge, a boundary between the lesions will be established so the LD of each individual lesion can continue to be measured. If the lesions have merged in a way that they can no longer be separated by this boundary, the newly merged lesion will be measured bi-dimensionally.

---

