## 8.4 COMPLETE RESPONSE

---

To satisfy criteria for a CR, all of the following criteria must be met:

- No evidence of new disease
- ALC in peripheral blood of  $<4 \times 10^9/L$
- Regression of all target nodal masses to normal size  $\leq 1.5$  cm in the LD
- Normal spleen and liver size
- Regression to normal of all nodal non-target disease and disappearance of all detectable non-nodal, non-target disease

- Morphologically negative bone marrow defined as <30% of nucleated cells being lymphoid cells and no lymphoid nodules in a bone marrow sample that is normocellular for age
- Peripheral blood counts meeting all of the following criteria:
  - ANC  $>1.5 \times 10^9/L$  without need for exogenous growth factors (e.g., G-CSF)
  - Platelet count  $\geq 100 \times 10^9/L$  without need for exogenous growth factors
  - Hemoglobin  $\geq 110 \text{ g/L}$  (11.0 g/dL) without red blood cell transfusions or need for exogenous growth factors (e.g., erythropoietin)

Subjects who fulfill all the criteria for a CR (including bone marrow criteria) but who have a persistent anemia, thrombocytopenia, or neutropenia or a hypocellular bone marrow that is related to prior or ongoing drug toxicity (and not to CLL) will be considered as a CR with incomplete marrow recovery (CRi).

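### The SPD limb of definitive PD has no size floor: target nodes that shrank to about 1.22 cm or less can reach PD on 1 to 3 mm of general growth while still normal, and not PD under Appendix A

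*Combined protocol and SAP*

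**What the plan says.** Section 8.7 opens with "The occurrence of any of the following events indicates definitive PD". The limbs that matter here are:

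- **Target SPD:** a rise of 50% or more "from the nadir in the SPD of target lesions". No minimum size or absolute increase is attached.
- **Single node:** a rise of 50% or more "in the LD of an individual node or extra-nodal mass that now has an LD of >1.5 cm and an LPD of > 1.0 cm".
- **New node:** "A new node that measures >1.5 cm in the LD and >1.0 cm in the LPD".
- **Spleen:** a rise of 50% or more in the enlargement, "with a minimum 2 cm increase and a minimum LVD of 14 cm". The liver limb has the same form, with a 20 cm minimum.

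Section 8.2.1 sets the reference: "The nadir LD of individual lesions and the nadir SPD will be used as references by which CLL progression will be characterized". It calls a node abnormal only above 1.5 cm. Section 8.4 asks for "Regression of all target nodal masses to normal size", meaning 1.5 cm or less in the LD.

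The introduction to Section 8 bases response and progression on the IWCLL criteria, judged by the treating investigator. Appendix A reproduces those criteria. Its PD list has no SPD limb; an existing site must grow by 50% or more in its greatest diameter. A note to Table 2 says there is no central radiology review.

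**The concern.** Each of the other measured limbs for nodes, spleen and liver in 8.7 combines a relative change with an absolute size, or uses an absolute size alone. The SPD limb is purely relative and is measured from the nadir. In a subject whose nodes have shrunk well, the nadir SPD is a sum of small products, and half of a small sum is a few millimetres of growth.

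Two contradictions follow. One scan can meet the nodal CR criterion in 8.4 and definitive PD in 8.7. The same scan can be PD under 8.7 and not PD under Appendix A.

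PD is an event for both PFS and DOR. The synopsis makes these primary for former Arm A; Sections 2.1 and 9.8.2 list them as secondary. PD also ends study treatment (Sections 4.4 and 6.3), so the contradiction reaches subjects as well as tables.

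**Working it through.** The plan states no figure on this point, so there is none to reproduce. Nadir sizes and measurement SDs below are assumptions; the thresholds come from 8.2.1, 8.4, 8.7 and Appendix A.

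**1. Growth needed.** PPD = LD × LPD, and SPD is the sum of the PPDs. If every target node grows in proportion, a 50% rise in SPD multiplies each diameter by √1.5 = 1.2247. For nadir diameter d (cm), the growth in mm is 10 × d × 0.2247.

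| Nadir diameter (cm) | Diameter at +50% SPD (cm) | Growth (mm) |
|---|---|---|
| 0.5 | 0.61 | 1.1 |
| 0.8 | 0.98 | 1.8 |
| 1.0 | 1.22 | 2.2 |
| 1.2 | 1.47 | 2.7 |
| 1.3 | 1.59 (no longer normal) | 2.9 |

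The nodes stay at or below 1.5 cm only if the nadir diameter is at most 1.5 / 1.2247 = 1.22 cm.

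**2. How many nodes must grow.** Take six nodes of 1.0 × 1.0 cm (SPD 6; PD at SPD 9). If k of them grow, each needs a PPD of (9 − (6 − k)) / k.

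| Nodes growing | PPD needed (cm²) | Diameter (cm) | Growth (mm) |
|---|---|---|---|
| 6 | 1.50 | 1.22 | 2.2 |
| 5 | 1.60 | 1.26 | 2.6 |
| 4 | 1.75 | 1.32 | 3.2 |
| 3 | 2.00 | 1.41 | 4.1 |
| 2 | 2.50 | 1.58 (abnormal) | 5.8 |
| 1 | 4.00 | 2.00 (abnormal) | 10.0 |

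**3. One subject under each rule.** Six nodes shrink from 2 × 2 cm (SPD 24) to 1 × 1 cm (SPD 6, down 75%), then grow to 1.22 × 1.22 cm (SPD 9, still 1 − 9/24 = 62.5% below baseline).

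- 8.7, SPD limb: +50%, so definitive PD.
- 8.7, single-node limb: LD up 22.5% and below 1.5 cm, so not met.
- 8.4, nodal criterion: all nodes at or below 1.5 cm, so met.
- Appendix A, PD: greatest diameter up 22.5%, short of 50%, so not met.

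The PR criteria in Appendix A also treat growth under 25% in nodes below 2 cm as not significant. That is a PR rule, so it is supporting evidence only.

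**4. Does another passage supply a floor?** The 1.0 cm measurability rule in 8.2.1 governs selection at baseline. Its 1.0 cm² default covers only sub-components of a split mass. The further evaluation described at the end of 8.7 concerns worsening during a treatment interruption. None of these limits the SPD limb.

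**5. Measurement error alone.** Model: true diameters constant; independent normal error on LD and LPD; five scans; nadir taken as the running minimum. A false PD is an SPD of at least 1.5 × the nadir with all nodes at or below 1.5 cm (60,000 replicates).

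| Target nodes | SD 1.0 mm | SD 1.5 mm |
|---|---|---|
| six, 1.0 cm | under 0.5% | about 0.5% |
| six, 0.8 cm | under 0.1% | about 4% |
| three, 1.0 cm | 0.3% | 8% |
| two, 0.8 cm | 9% | 38% |
| three, 0.6 cm | 14% | 45% |

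At an SD of 0.5 mm every row is about zero. With three scans instead of five, the last row falls to 5% and 21%. On the minimum schedule five scans are Cycles 3, 6, 12, 24 and 36, or 36 × 28 = 1,008 days.

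**The case against.** Four stronger readings are tempting, and the documents support none of them.

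- **Any responder progresses after 2 mm.** This needs a nadir of about 1.22 cm or less and growth across most target nodes. With six 1.0 cm nodes, growth confined to one or two makes a node abnormal first.
- **Measurement noise will produce many false progressions.** The high rates come from two or three very small nodes and assumed SDs. Six nodes of 1.0 cm give under 1%. The documents give no measurement error, node counts or nadir sizes, and nothing supports independent errors.
- **The plan leaves open whether CR or PD applies.** The opening of 8.7 admits no exception, 8.8 allows PD at any time point, and 8.3 ends best overall response at progression, so the text points to PD. The overlap is also with one CR criterion only; 8.4 further requires marrow, lymphocyte count, blood counts and organ size. What remains is that 8.5 bars PR when worsening meets PD and 8.4 has no matching item.
- **The response rate is distorted.** Nothing here shows a change in ORR, the primary variable in 9.8.1.

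Copying the single-node floor into the SPD limb is not an innocent repair. Six nodes growing from 0.6 to 1.4 cm (SPD 2.16 to 11.76, +444%) would then not count. Because PD stops treatment, the threshold is a clinical rule for the sponsor.

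Finally, the study is descriptive, with no hypothesis test or power calculation (9.1, 9.2). That lowers the severity but does not remove the contradiction.

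**Conclusion.** The concern holds in a conditional form. The missing floor, and the conflict between 8.7 and Appendix A, are matters of text and depend on no assumption. The 1 to 3 mm figure is exact geometry, given nadir diameters from 0.5 cm to about 1.22 cm and roughly uniform growth in both diameters of all target nodes; it rises to 3.2 mm from 1.0 cm if four of six grow.

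Any false events would fall mainly on good nodal responders and would shorten PFS and DOR. Their frequency is unknown: from under 1% to about 45% over five scans in the scenarios tried at 1.0 to 1.5 mm, and about zero at 0.5 mm. These rates show sensitivity to the assumptions and do not predict what this study will see. The point is of moderate importance.

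**What to change.** **Text.** The sponsor should reconcile 8.2.1, 8.4, 8.7 and Appendix A on growth in nodes that remain normal. One sentence should say which category applies when the nodal CR criterion and the SPD limb are both met. Which rule governs stopping treatment is the sponsor's choice.

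**Analysis.** Flag each progression that rests on the SPD limb alone with all target nodes at or below 1.5 cm in LD. Report PFS and DOR with and without counting these as events. The LD and LPD are already recorded under 8.2.1. Establishing that no other limb was met uses the organ, new-lesion, non-target and blood-count assessments.

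**Cost.** A clarifying amendment and a small amount of programming. In the version without these events, some progressions will be dated at a later assessment, up to 12 cycles (12 × 28 = 336 days) later after Cycle 12. Table 2 schedules no tumor evaluations once a subject is off treatment for PD, so subjects without a later assessment would be censored at the flagged scan. That version is therefore a sensitivity analysis and should not replace the main one.

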## 8.8 NON-EVALUABLE

---

In a subject who does not have evidence of PD, the occurrence of any of the following conditions indicates a response status of NE:

- There are no images or inadequate or missing images

- Images of the liver and spleen are missing at that time point (with the exception that absence of splenic images will not result in an NE designation in a subject known to have undergone splenectomy).

A time-point will be considered to have a response of NE if any target lesion is missing. PD may be assigned at any time point regardless of the extent of missing target or non-target lesions. Missing non-target lesions will not impact the ability to assess for response or disease progression.

## 8.9 LYMPHOCYTOSIS DURING THERAPY

---

Upon initiation of umbralisib, a temporary increase in lymphocyte counts (i.e.,  $\geq 50\%$  increase from baseline and above absolute lymphocyte count of 5,000/mcL) may occur. The onset of isolated lymphocytosis usually occurs during the first few weeks of umbralisib therapy and usually resolves within three to four months. Subjects with lymphocytosis should be continued on study drug until the occurrence of definitive disease progression (i.e., disease progression that is manifest by worsening CLL-related signs other than lymphocytosis alone), or the occurrence of another reason to discontinue study therapy.

## 9 STATISTICAL CONSIDERATIONS

---

This section describes the statistical methods to be used to analyze the efficacy and safety endpoints.

### 9.1 SAMPLE SIZE

---

As no formal hypothesis testing is being conducted in this study, the sample size is not based on powering for any study objectives. Subjects from Treatment Arms B, C and D in Study 304 may enter this study upon documented progression of disease as confirmed by the independent central radiology review group. At the end of the study, non-progressed subjects from Treatment Arm A may also be enrolled to this Phase 2 Companion Study. It is undetermined the number of subjects that may enter this Companion Study, however it may not exceed the total number of subjects that have enrolled in Study 304, which may be up to approximately 700 subjects.

### 9.2 GENERAL ANALYSIS CONVENTION

---

The primary objective of this compassionate use study is to allow subjects progressing in Arms B, C, and D of [study UTX-TGR-304](#) to receive, and for subjects previously in Arm A to continue to receive, combination therapy with ublituximab plus umbralisib. As the study is primarily observational, no formal hypothesis testing will be conducted. Continuous data will be described using the following descriptive statistics: n, mean, median, minimum and maximum. Data will be displayed in all listings sorted by treatment group (based on the treatment arm the subject was on in Study 304) and subject number.

When count data are presented, the percentage will be suppressed when the count is zero in order to draw attention to the non-zero counts. A row denoted "Missing" will be included in count tabulations where necessary to account for dropouts and missing values. Unless otherwise specified, the denominator for percentages will be the number of subjects with a non-missing assessment in a given treatment group within the analysis population of interest.

### 9.3 ANALYSIS POPULATIONS

---

The Intent-to-Treat (ITT) population will consist of all subjects who were enrolled and have at least one post-treatment efficacy measurement. Primary efficacy analyses will be performed based on the ITT population.

The Safety Population will include all subjects who were enrolled and received at least one dose of study drug. All safety assessments including toxicity will be performed on the Safety Population.

The Per-Protocol Population (PP) will consist of all ITT subjects without a major protocol deviation. The criteria for a major protocol deviation will be determined and documented prior to data base lock. Subject exclusion from the PP population will also be determined and documented prior to database lock. Supportive analyses may be performed based on the PP population.

Furthermore, in the analyses/summaries, subjects will be assigned a treatment group based on the treatment they received on study UTX-TGR-304 prior to their entering of this Companion Study as appropriate.

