## 5 STUDY ASSESSMENTS AND TREATMENT SCHEDULE

The table below lists all of the required assessments that should be performed at each study visit.

TABLE 1: STUDY ASSESSMENT AND TREATMENT SCHEDULE

Cycle (C) = 28 days	Screening 	Cycle 1 				Maintenance 		Cycles 15+ 	End of study	
						Cycles 2 - 6	Cycle 9 & 12			
Procedure \ Days (D)	-28-0	D 1	D 2	D 8	D 15	Day 1	Day 1	Q 3 cycles		
Medical History	X									
Rai Staging	X									
ECOG performance status	X	X			X	X	X	X	X	
Physical examination	X	X		X	X	X	X	X	X	
Vital signs (pulse, BP, temp)	X	X		X	X	X	X	X	X	
BM aspirate/biopsy 	X									
Serum Pregnancy Test 	X									
Urine Pregnancy Test 						X	X	X	X	
Hematology 	X 	X	X	X	X	X	X	X	X	
Serum Chemistry	X 	X		X	X	X	X	X	X	
FISH Panel 	X									
Tumor evaluation 	X	Evaluations are to be obtained during cycles 3, 6 & 12. Following cycle 12, evaluations should occur at least every 12 cycles								
Serology: HCV, HBV, CMV 	X									
CMV Surveillance						X 	X	X 		
MRD 						For subjects in PR or CR beginning at the Cycle 6 response assessment				
Ublituximab 		X	X 	X  5	X 	X	X	Q3 months		
Umbralisib (TGR-1202) Dose		Days 1 - 28 (Daily)								
Adverse events (CTC v4.0)		Throughout the study								X 
Concomitant Medication		Throughout the study								X

 Tests that have already been completed as part of the requirements for UTX-TGR-304 may be used to evaluate eligibility for this companion study

 Treatment Administration +/- 1 day window. Physical Exam, Vital Signs, ECOG PS, Hematology and Serum Chemistry visit days have - 1 day window

 Treatment Administration +/- 3 day window Cycles 2-6. Physical Exam, Vital Signs, ECOG PS, Hematology and Serum Chemistry visit days have a - 3 day window during Cycles 2 through 6. Treatment Administration +/- 7 day window after Cycle 6. Physical Exam, Vital Signs, ECOG PS, Hematology and Serum Chemistry visit days have a - 7 day window for all cycles after cycle 6

 Treatment Administration +/- 7 day window. Physical Exam, Vital Signs, ECOG PS, Hematology and Serum Chemistry visit days have a - 7 day window for all cycles after cycle 6

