 Unilateral bone marrow aspirate and/or biopsy performed at investigator discretion in subjects for whom assessment of extent of CLL involvement and bone marrow cellularity is important. In addition, a post-baseline bone marrow biopsy should be completed to confirm potential CR by radiological assessment.

 For women of child bearing potential, completed within 3 days of Cycle 1 Day 1.

 For women of child bearing potential, completed within 3 days of visit

 Must be obtained prior to ublituximab administration if on day of infusion.

 Must be done within 14 days of cycle 1 day 1

 For del(13q), del(11q), del(17p), and (12) trisomy, t(11:14)

 Scans should be completed approximately 45 days prior to Day 1 of Cycle 1. Radiology assessment should include CT or MRI imaging of chest, abdomen, and pelvis.

 Serum virology to include HBsAg, HbC antibody, HCV antibody and CMV IgG and IgM. If HbC antibody, HCV antibody or CMV IgM is positive, subjects must be evaluated for the presence of active HBV, HCV or CMV by PCR

 Q3 months CMV screening by PCR for all subjects.

 Peripheral blood sample may be analyzed by local lab. For subjects MRD negative by peripheral blood, a bone marrow should be completed to confirm MRD negativity. If a bone marrow is not completed, another peripheral blood sample should be collected to confirm the MRD negativity at least 12 weeks later. MRD should continue to be evaluated for subjects with PR/CR at response assessment intervals until 2 consecutive peripheral blood MRD negative results, or 1 negative peripheral blood MRD and 1 negative bone marrow MRD are observed.

 Subjects who received ublituximab on UNITY-CLL trial (Arm C), will not receive split dosing on Day 1 and 2 of cycle 1. Subjects should receive full dose on Cycle 1, Day 1 and will not receive Day 8, and 15 during Cycle 1.

 If clinically significant adverse event or abnormal result is observed that is not resolved by the end-of treatment visit, continue to monitor and record up through 30 days after study drug discontinuation.

TABLE 2: FOLLOW UP ASSESSMENTS SCHEDULE

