## 8 MEASUREMENT OF EFFECT

---

During the study period, all subjects will be evaluated for response by CT and/or MRI. Evaluations are to be obtained at approximately cycles 3, 6 and 12. Following cycle 12, evaluations should occur at least every 12 cycles unless clinically indicated more frequently. The determination of response and progression will be based on IWCLL criteria (Hallek M, 2008) by the treating investigator.

CT scan is the preferred method of tumor assessment, but MRI may be used at the investigator's discretion. The same method of assessment and the same technique should be used to characterize each identified and reported lesion at baseline and throughout the study. All baseline assessments to characterize disease will be performed within approximately 45 days of Cycle 1 Day 1, prior to initiation of therapy.

Subjects should remain on study treatment until the occurrence of definitive disease progression, unacceptable toxicity, or withdrawal from the study due to investigator decision or other reasons. Subjects who discontinue from study treatment (either for toxicity or physician choice) and have not progressed will continue to be followed for progression as per the protocol.

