## 9.8 EFFICACY ANALYSES

---

All subjects included in the study must have a baseline tumor assessment within 30 days of Cycle 1/Day 1 and at least one post-treatment efficacy evaluation in order to be included in the efficacy analyses. Each subject will be assigned one of the following categories: 1) complete response, 2) partial response, 3) stable disease, 4) progressive disease, 5) early death from malignant disease, 6) early death from toxicity, 7) early death because of other cause, or 9) unknown (not assessable, insufficient data).

---

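### The set labelled Intent-to-Treat requires a post-treatment efficacy result, which can raise but never lower ORR in Arms B, C and D; the 30-day baseline rule also conflicts with the 45-day scan window

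*Combined protocol and SAP*

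**What the plan says.** **Who is analysed.** Section 9.3 defines the Intent-to-Treat population as one that "will consist of all subjects who were enrolled and have at least one post-treatment efficacy measurement" and bases the primary efficacy analyses on it. Section 9.8 repeats the condition for efficacy as a whole: subjects need "at least one post-treatment efficacy evaluation in order to be included in the efficacy analyses".

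**What they are assigned.** The same paragraph of 9.8 continues: "Each subject will be assigned one of the following categories". The list includes "5) early death from malignant disease, 6) early death from toxicity, 7) early death because of other cause", and ends with a class for subjects who cannot be assessed.

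**Denominators.** Section 9.2 provides a row for missing values in count tables but by default takes percentages over subjects with a non-missing assessment. Section 9.8.1 plans ORR with a one-sided 90% interval and does not name its denominator. Section 9.4 reports how many subjects were treated and how many are in the ITT set.

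**Baseline window.** Section 9.8 states: "All subjects included in the study must have a baseline tumor assessment within 30 days of Cycle 1/Day 1". Table 1, footnote 11, states: "Scans should be completed approximately 45 days prior to Day 1 of Cycle 1". Section 8 states: "All baseline assessments to characterize disease will be performed within approximately 45 days of Cycle 1 Day 1". Section 5.1 also sets the scan limit at 45 days. Table 1, footnote 1, adds: "Tests that have already been completed as part of the requirements for UTX-TGR-304 may be used to evaluate eligibility for this companion study".

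**Arm A.** The synopsis makes PFS and DOR, not ORR, primary for former Arm A subjects. Section 9.8.2 starts their PFS at randomization in Study 304 and, unless their best response there was stable disease, their DOR at the first response in that study.

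**The concern.** A set whose membership depends on a post-treatment observation is a response-evaluable set, not an intent-to-treat set. The early-death and unassessable categories in 9.8 exist to hold subjects without an evaluable response, but the sentence before them removes anyone with no post-treatment evaluation. The plan never says whether such a subject counts in the ORR denominator, so two statisticians could report different rates from the same data.

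The term for the qualifying measurement is undefined, and the size of the problem depends on it. If only imaging counts, anyone lost before the Cycle 3 scan is excluded. If blood counts count, almost nobody is.

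The baseline rule is a separate defect. A subject scanned on days 31 to 45 follows the schedule yet fails the 9.8 entry rule. The 9.3 definition has no 30-day condition, so 9.3 and 9.8 also describe different efficacy sets.

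At stake are the headline ORR, CR and PR rates with their lower limits, and the PFS curve for Arms B, C and D. No hypothesis is tested, so type I error and power are not affected.

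**Working it through.** **Inputs.** From the documents: 28-day cycles and a first scheduled tumor evaluation in Cycle 3 (Table 1), and a one-sided 90% interval for ORR (9.8.1). The documents give no loss rate, expected ORR, powered sample size or expected median PFS, so there is no planned figure to reproduce. Every size below rests on a stated assumption.

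**1. Direction for ORR, Arms B, C and D.** Let X be responders, N all treated subjects, m those without a post-treatment measurement, and f = m/N. None of the m can be a recorded responder, so

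reported ORR = X/(N − m) = (X/N)/(1 − f) ≥ X/N,

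with equality only if X = 0 or m = 0. A check of every integer combination for N = 2 to 119 found no exception.

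**2. How large f could be.** Cycle 3 runs from day 2×28+1 = 57 to day 3×28 = 84, so losses build up over k = 2 to 3 cycles if only imaging qualifies. With an assumed loss r per cycle, f = 1 − (1 − r)^k:

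| r per cycle | k = 2 | k = 3 |
|---|---|---|
| 1% | 1.99% | 2.97% |
| 2% | 3.96% | 5.88% |
| 4% | 7.84% | 11.53% |

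If hematology qualifies, Table 1 schedules it from Cycle 1 Day 2 and f is near 0.

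**3. Effect on ORR.** The last column assumes 100 treated and 40 responders (Clopper-Pearson, one-sided 90%).

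| f | All-treated 40% reported as | All-treated 50% reported as | Lower limit, 40 responders |
|---|---|---|---|
| 0 | 40.0% | 50.0% | 33.4% (40/100) |
| 2% | 40.8% | 51.0% | 34.1% (40/98) |
| 5% | 42.1% | 52.6% | 35.3% (40/95) |
| 10% | 44.4% | 55.6% | 37.3% (40/90) |

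**4. PFS, Arms B, C and D.** The clock starts at study entry, so removing an early death raises the Kaplan-Meier curve from that death onward. Ten invented subjects: a death at month 1, progressions at months 6 and 12, seven censored at month 24. S(12) = 9/10 × 8/9 × 7/8 = 0.700; without the early death it is 8/9 × 7/8 = 0.778.

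As a bound, suppose every lost subject is an immediate death and PFS in the rest is exponential with an assumed median of 12 months. Solving (1 − f) × 2^(−t/12) = 0.5 gives an all-treated median of t = 12 × (1 + log2(1 − f)): 11.65, 11.11 and 10.18 months for f = 2%, 5% and 10%.

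**5. PFS, Arm A.** Here an early death in this study falls late on the Study 304 clock. Ten invented subjects: progressions at 30 and 30 months, a death at 49, seven censored at 60. With everyone included, S(36) = 8/10 = 0.800 and S(50) = 0.800 × 7/8 = 0.700. Without the death, both are 7/9 = 0.778. The estimate falls at 36 months and rises at 50, so no direction can be stated for Arm A or for pooled PFS.

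**6. The 30-day rule.** Days 31 to 45 are 15 of the 45 allowed days, one third of the window. This rule can remove responders as well as non-responders. With an assumed 100 subjects and 50 responders, removing 20 gives anything from 30/80 = 37.5% to 50/80 = 62.5%. The direction is unknown.

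**The case against.** The strongest reply is that the contradiction depends on how the undefined term is read. Sections 8.1 to 8.5 use physical examination and blood counts as well as imaging, and Table 1 schedules both in Cycle 1. On that reading most early deaths have a post-treatment measurement, stay in the set and fill their categories. Sections 8.3 and 8.8 also provide a not-evaluable response, and a subject so coded is not clearly missing under 9.2. Every size above is assumed. The study is a descriptive compassionate-use extension with no decision tied to ORR, and the counts in 9.4 let a reader divide responders by treated subjects. Footnote 1 of Table 1 permits reuse of Study 304 tests for eligibility and does not expressly make them the response baseline.

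Much of this stands. The loss may be near zero, the consequence is descriptive, and 9.2 is better seen as an ambiguity than as a second exclusion. That older scans will be used is an inference.

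It does not remove the point. The entry rule has no exception for early deaths, and a not-evaluable category does not say who is in the denominator. Recomputing from 9.4 works only in part: the 30-day rule can drop responders, and disposition counts do not recover a PFS curve. The conflict between 30 and 45 days holds however the term is read.

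**Conclusion.** The point holds and should be fixed. The primary set is mislabelled and its entry rule conflicts with the outcome categories in the same paragraph. For Arms B, C and D the rule cannot lower ORR, CR or PR rates and raises them whenever there are both responders and exclusions. On an assumed all-treated ORR of 40% or 50%, losses of 2% to 10% add 0.8 to 5.6 percentage points; the effect is close to nil if Cycle 1 blood counts qualify. For PFS in those arms, the bound is an all-treated median of 10.2 to 11.7 months against an assumed reported 12. For Arm A and pooled PFS the direction is undetermined, as is the effect of the 30-day rule. Confidence is high in what the text says. The sizes are illustrations, and no bias in actual data is claimed.

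**What to change.** - **Primary set (9.3, 9.8).** Use all enrolled subjects who received at least one dose, and drop the post-treatment-evaluation condition. Keep the present set as a supportive analysis labelled response-evaluable.
- **Arms B, C and D.** Count early death, not evaluable, unknown and missing as non-response for ORR, CR and PR, and keep early deaths as PFS events.
- **Arm A.** Keep all treated subjects in PFS and DOR under the 9.8.2 definitions, and do not impute ORR non-response over a response carried from Study 304.
- **Definitions.** State what counts as an efficacy measurement, and say in 9.2 that the non-missing denominator does not apply to response rates.
- **Baseline window.** Reconcile the 30-day rule in 9.8 with the 45-day window in Table 1, 5.1 and Section 8, so that a scan done on schedule does not by itself exclude a subject.

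The cost is a few sentences in 9.2, 9.3 and 9.8 and no new data collection. Response figures may come out slightly lower.
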